5. HYPOTHESIS AND RESEARCH QUESTION

The hypothesis is that an exclusive human milk diet compared with exposure to cow milk results in differences in a) gut bacteria (types and diversity), b) stool and urine metabolites, and c) body composition. We will address the research question "In infants born <30 weeks completed gestational age (Population), what is the effect of an exclusive human milk diet (Intervention) compared to a current standard diet using cow milk derived products (Control) on gut bacteria, metabolites and body composition at near term/term (Outcomes).

6. TRIAL OBJECTIVES

- 381 To evaluate whether an exclusive human milk diet compared with exposure to cow's milk
- results in differences in:
- 6.1. Gut microbiota: gut bacterial diversity, proportions of specific taxa, eg Bifidobacteria
- 384 species
- 385 6.2. Metabolomics: Gut derived metabolites and markers of gut function; metabolites
- include stool Volatile Organic Compounds (VOC, using Gas Chromatography MS),
- and urine (using 1H NMR and/or Liquid Chromatography MS). Markers of gut health
- may include those measured in the stool (e.g. calprotectin) and urine (e.g. intestinal
- fatty acid binding protein, iFABP)
- 390 6.3. Body composition: assessed using whole body magnetic resonance imaging (MRI)
- 391 6.4. Immune markers in the blood (lymphocyte subsets) and plasma amino acid levels.

392 393

380

7. TRIAL DESIGN

- This will be a randomised open label, controlled trial in at least two UK centres. Eligible
- preterm infants include those where a) mothers intend to provide their own breast milk or b)
- are medically unable to provide breast milk but are happy for their infant to join the study.
- Less than 10% of all infants do not receive their mother's milk. Our data show that < 5% of
- mothers do not wish their baby to receive breast milk. Approximately 5% of mothers are
- medically not able to provide their own milk: this includes those who are HIV positive, are
- 400 very sick or receiving chemotherapy (or similar) treatment. Infants will be randomised as
- 401 soon as possible and no later than 72 hours to receive either standard preterm formula or
- 402 exclusive human milk to make up any shortfall in mother's own milk (MOM).
- 403 Supplementation will begin if there is insufficient MOM at any point between 48 72 hours
- after birth to enable feeding according to the trial feed advancement protocol (Appendix 1).

405

- 406 Our data show that almost every infant (>95%) born to mothers who intend to provide their
- 407 own MOM, actually receive some MOM, but occasionally MOM is not available until after
- 48 hours of age. Infants will remain eligible for trial inclusion, and remain part of the trial
- 409 until 34 weeks corrected age regardless of the amount of MOM provided. An infant will
- 410 therefore be eligible if they have not received any MOM. Our data show that in these infants

- 411 MOM will typically provide between 30% and 100% (average around 60-70%) of intake 412 requirements over the first few weeks. The trial will record the duration that an infant 413 receives MOM. The trial is designed to assess the impact of an exclusive human milk diet on 414 gut bacteria and metabolites, therefore the primary analysis will be valid regardless of the 415 proportion of milk intake provided as MOM. Fortifier (human or bovine) will be added to 416 MOM when an enteral intake of at least 150 ml/kg/day is achieved. For practical reasons 417 fortifier will be added when a minimum quantity of 50 ml of MOM is available. Infants will 418 receive the allocated diet until 34 weeks postmenstrual age. At 34 weeks PMA trial 419 intervention will be weaned over a period of approximately four days.
 - 7.1 Exclusive human milk arm: MOM; 'Ready to Feed Human Preterm 26' formula (Prolacta) will be used to make up any shortfall in MOM before 150 ml/kg/day of enteral feeds is reached to allow for nutrient equivalence with preterm formula in the standard arm; once 150 ml/kg/day enteral feed is reached human milk-based fortifier will be added when at least 50 ml of MOM is available. If there is less than 50 ml of MOM available, the balance will be made up with 'Ready to Feed Human Preterm formula 26'. The maximum routine enteral intake will be 165 ml/kg/day providing a protein intake of 3.7- 4.6 g/kg/ day, carbohydrate intake of 8.2 12.2 g/kg/day and fat intake of 8.2 9.2 g/kg/day.
 - 7.2 Standard arm: MOM; standard preterm formula will be used to make up any shortfall in MOM before 150 ml/kg/day of enteral feeds is reached; once 150ml/kg/day enteral feed is reached standard breast milk fortifier will be added when at least 50 ml of MOM is available. The maximum enteral intake will be 165 ml/kg/day providing a protein intake of 3.7 4.6 g/kg/day, carbohydrate intake of 13 14.7 g/kg/day and a fat intake of 6.3 6.4 g/kg/day. Specific products (i.e. brand and type of preterm formula and bovine fortifier) used will be determined by standard practice in each neonatal unit.

8. TRIAL ENDPOINTS

- The outcomes assessed in infants recruited at both sites will be microbiota and metabolomics.
- 438 Infants recruited at Chelsea and Westminster NHS Foundation Trust will be additionally be
- 439 assessed for body composition. Infants recruited in Newcastle will have additional blood
- samples collected and stored for future studies.

441

420

421

422

423

424

425

426

427

428

429

430

431

432

433

434 435

436

- 442 8.1. Primary endpoints
- 8.1.1. Newcastle and Chelsea and Westminster NHS Foundation Trust Hospitals
- 444 8.1.1.1. Stool gut microbiota: Next Generation Sequencing using MiSeq
- 445 8.1.2. Chelsea and Westminster NHS Foundation Trust (Imperial College London)
- 8.1.2.1. Body composition at term equivalent age assessed with whole body Magnetic
- Resonance Imaging (MRI) at 37-42 weeks postmenstrual age
- 448 **8.1.3.** Newcastle
- 8.1.3.1. Salvaged blood for growth factors e.g. IGF-1
- 450 8.1.3.2. Targeted blood: plasma amino acid (PAA) profiles and lymphocyte subsets.

- 452 8.2. Secondary endpoints
- 453 8.2.1.1. Stool metabolomic profile using GC-MS for VOCs
- 454 8.2.1.2. Urine metabolomic profile using LC-MS or NMR
- 455 8.2.1.3. Markers of gut health e.g. urinary intestinal fatty acid binding protein (iFABP)
- and stool calprotectin, using standard biochemical techniques
- 8.2.2. Feeding related outcomes: total number of days on which feeds were withheld on any
- 458 occasion after trial enrolment determined by days of parenteral nutrition (PN); age when
- 459 enteral feeds ≥150ml/kg/day maintained for at least 3 days (coded as age at last PN); total
- days exposed to MOM prior to 34 weeks; feeding mode at discharge (breast, formula or
- 461 mixed)
- 462 8.2.3. Healthcare resource use: total length of stay (days); postmenstrual age at discharge;
- 463 days in intensive, high-dependency and low-dependency care according to national
- 464 definitions (BAPM)
- 8.2.4. Neonatal morbidities and clinical outcomes: survival to discharge; Retinopathy of
- 466 Prematurity requiring intervention; Necrotising Enterocolitis requiring surgery or leading to
- death; blood-culture positive sepsis; total days when any antibiotic administered; chronic
- 468 lung disease (oxygen requirement or need for any pressure support at 36 weeks postmenstrual
- age), peri-ventricular haemorrhage (PVH) and/or presence of parenchymal damage. These
- 470 will all be determined using established national definitions (National Neonatal Audit
- 471 Programme), and informed using our recently completed studies on NEC[9] and agreed
- where necessary by investigator end-point review committee.

473	8.2.5.	Weight, head circumference and length measured on a weekly basis where possible
474	8.2.6.	Residual samples will be stored in the HTA and REC approved Great North Neonata
475	Bioba	nk (Newcastle Biomedicine Biobank)
476		
477	9. PA	ATIENT POPULATION
478	9.1.	Inclusion criteria
479	9.1.1	Preterm infants < 30 completed weeks gestation following signed parent consent
480		[Note protocol modification April 2018 after 25 recruits to extend eligibility criteria
481		from <29 weeks gestation to <30 weeks gestation]
482	9.1.2	Have not received any milk other than MOM
483	9.1.3	Less than 72 hours of postnatal age [Note protocol modification April 2018 after 25
484		recruits to extend eligibility criteria <48 hours age to <72 hours age]
485	9.2.	Exclusion criteria
486	9.2.1	Lack of informed consent, or where the attending medical team feel it is inappropriate
487		for other reasons e.g. social or child protection issues, severely unwell and/or not
488		predicted to survive
489	9.2.2	Infant who has received any formula or bovine milk product prior to enrolment
490	9.2.3	Participation in another study will not be an absolute exclusion as this is a
491		mechanistic study, and will be assessed on a study-by-study basis; trials using
492		interventions that are anticipated to have similar mechanisms of action on the key
493		outcomes (gut bacteria and body composition) will be excluded (e.g. infants enrolled
494		to this study will not be eligible to join the trial of enteral lactoferrin (ELFIN) and
495		vice versa). However, where there is no scientific basis to exclude an infant i.e. the
496		trial intervention is not anticipated to either interact with the diet, or impact on the
497		primary outcomes of gut bacteria or body composition, or is purely observational in
498		nature, then study participation will be offered to parents. This view has been
499		developed based on our research experience and feedback from parents; some parents

may themselves have been involved in studies or medicines trials during this

deny parents the opportunity to participate in a study they view as potentially beneficial; our recently completed in-depth qualitative study funded by the UK

pregnancy that may impact on neonatal outcomes; it might be considered un-ethical to

500

501

502

503

504 National Institutes of Health Research (PARENT) involved interviewing parents of 505 preterm infants who had been enrolled in more than one study. This showed that 506 parents were aware of and supported the possible need for infants to be enrolled in 507 more than one study. 508

9.2.4 Infants likely to be discharged or transferred to another hospital before 34 weeks postmenstrual age.

510 511

512

513

514

515

516

517

518

519

520

521

509

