- would ordinarily be discarded). These will be stored for biobanking [10].
- 11.2.3 Targeted blood samples (Newcastle only): With specific parent consent (that would
- not otherwise preclude ongoing trial participation) we will also take two targeted blood
- samples: 1) after feeds of 150mls/kg/day have been established for at least 3 days and 2) prior
- to trial cessation i.e. around 33-34 weeks postmenstrual age. Targeted blood samples will be
- taken at the same time as any blood samples required for clinical reasons so will not involve
- additional venepuncture.
- 610 11.2.4 Body Composition (Imperial only): at 37-42 weeks postmenstrual age assessed with
- 611 whole body MRI

- 613 11.3 Data
- 614 11.3.1 At randomisation
- Date and time of birth
- 616 Sex
- Confirmation of eligibility (full eligibility check)
- Date of parental consent
- Name of person taking consent
- Gestational age (in weeks and days)
- Recruiting hospital
- 622 Study allocation
- 623 11.3.2 Baseline evaluation
- Birth weight (kg)

625 Birth length (cm) • 626 Head circumference (cm) 627 Ethnicity (NHS Ethnicity) 628 Mode of delivery 629 Use of antenatal steroids 630 Date and time first trial intervention administered 631 11.3.3 Daily evaluations 632 Record nutritional intake (type of feed, parenteral nutrition or formula as applicable) • 633 Level of care (BAPM 2010) 634 If infant is nil by mouth and reason 635 Check for SAE 636 Record of withdrawal information if relevant 637 11.3.4 Weekly evaluations 638 Weight (kg) 639 Length (cm) 640 Head circumference (cm) 641 11.3.5 End of study evaluation 642 Weight (kg) 643 Length (cm) 644 Head circumference (cm) 645 Whole body MRI 646 647 11.4 Investigations 648 11.4.1 Stool microbiome

We will analyse bacteria DNA extracted from stool samples using our well-established protocols and 16S ribosomal RNA methods that are effective tools to explore the diversity of bacterial communities (Stewart et al. 2012). Using the MiSeq high throughput analyzer we will incorporate 188 samples as well as necessary controls, which we have found to be the optimum number of samples to obtain coverage of the bacterial community.

654

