12 PHARMACOVIGILANCE

- As this is not a clinical trial of a medicinal product and the intervention, and its delivery, are considered safe and already in universal use we do not anticipate any adverse reactions due to the trial intervention (use of donor breast milk products). However, this is a very high risk patient group and some infants may develop serious complications e.g. sepsis, and some may die. We will record all serious adverse events (SAE). Serious adverse events that may occur include:
- Outcomes recorded and reported as part of the study: necrotising enterocolitis (NEC), sepsis, intraventricular haemorrhage, periventricular leukomalacia, retinopathy of

- prematurity, chronic lung disease, feeding intolerance (number of days when nil by mouth i.e. no enteral intake and need for parenteral nutrition), antibiotic exposure (number of days on which an antibiotic was administered) and death.
- 719 Outcomes that commonly occur in this population but that will not be specifically 720 recorded or reported as part of this study include: abnormal electrolytes, bone 721 chemistry, liver functions tests or other routine biochemistry or haematology; 722 transfusion of blood or related products; complications related to use of intravenous 723 catheters (e.g. misplacement or malfunction); presence of and/or treatment for a patent 724 ductus arteriosus; requirement for surgery and/or provision of an intestinal or airway 725 stoma, intraventricular shunt; vomiting, gastro-oesophageal reflux, constipation, 726 diarrhoea, skin or nappy rash.

731

732

733

734

735

736

737

738

739

740

741

742

743

744

745

728 13 STATISTICAL CONSIDERATIONS

729 13.1 Sample size calculation

730 13.1.1 Gut bacteria

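### Two secondary feeding outcomes in Protocol 8.2.2 are coded from parenteral nutrition and do not measure what they are named for

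*Protocol*

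**What the plan says.** Protocol 8.2.2 lists four feeding outcomes, two of them coded from PN. The first is the "total number of days on which feeds were withheld on any" "occasion after trial enrolment determined by days of parenteral nutrition (PN"). The second is the age at full feeds: "enteral feeds ≥150ml/kg/day maintained for at least 3 days (coded as age at last PN"). The first does not require that enteral intake was zero. The second does not limit the last PN to a first course or to a time window.

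Section 12 lists, among outcomes to be recorded and reported, "feeding intolerance (number of days when nil by mouth i.e. no enteral intake and need for parenteral nutrition"). That wording needs both no enteral intake and PN.

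Section 11.3.3 lists what is collected each day. It includes "If infant is nil by mouth and reason" and "Record nutritional intake (type of feed, parenteral nutrition or formula as applicable"). Enteral volume is not named there.

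**The concern.** In each case the protocol states a concept and then fixes a coding that measures something else. This is not detail left to a later analysis plan, because 8.2.2 sets the coding itself.

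PN can run while feeds are being given and increased, so a PN day is not a day on which feeds were withheld. The last PN day marks full feeds only if PN stops exactly when full feeds are reached and is never restarted. Followed literally, the plan would report a count of withheld days that is largely ordinary advancement, and an age at full feeds that may really be the end of a late illness. Section 4.4 says that clinical data from the trial might go into future meta-analyses, where the named concepts would be taken at face value.

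**Working it through.** No power or sample size figure is attached to these outcomes, so there is none to reproduce. The check is a day count on the protocol's own feeding schedules, followed by a comparison of definitions.

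**Inputs (Appendix 1 and section 7)**
- Chelsea and Westminster, 29+6 weeks or below: start at 15 ml/kg/day, add 15 once a day; optionally add 15 twice a day (30 per day) once 60 is tolerated.
- Newcastle: start at 10 to 20 ml/kg/day, add 24 per day.
- Enrolment: at the latest 72 hours after birth, taken here as day 1 to day 4.

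**Assumptions, not in the protocol:** feeds start on day 1 and are never interrupted; PN runs from enrolment until a stated enteral volume is reached, and the last PN day is the day before.

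**Day on which 150 ml/kg/day is reached**
- Chelsea and Westminster, once daily: 15 + 15(d − 1) ≥ 150 gives d = 10.
- Chelsea and Westminster, faster from 60: 15, 30, 45, 60, 90, 120, 150 gives d = 7.
- Newcastle: (150 − 10)/24 = 5.8 or (150 − 20)/24 = 5.4, so 6 steps after day 1 and d = 7.

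**PN days scored as withheld = d − e**, where d is the day the stop volume is reached and e is the enrolment day. Each cell gives enrolment on day 1 / day 4.

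| Schedule | PN to 100 | PN to 120 | PN to 135 | PN to 150 |
|---|---|---|---|---|
| C&W once daily | 6 / 3 | 7 / 4 | 8 / 5 | 9 / 6 |
| C&W faster from 60 | 5 / 2 | 5 / 2 | 6 / 3 | 6 / 3 |
| Newcastle, start 10 | 4 / 1 | 5 / 2 | 6 / 3 | 6 / 3 |
| Newcastle, start 20 | 4 / 1 | 5 / 2 | 5 / 2 | 6 / 3 |

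With PN to 150 the range is 3 to 9 days; with PN to 100–135 it is 1 to 8. On the section 12 wording the same infant scores 0, because feeds were given every day.

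**Age at last PN compared with the day 150 is first reached.** The gap is the day 150 is reached minus the last PN day. The longest is 10 − 6 = 4 days (C&W once daily, PN to 100). The shortest is 7 − 6 = 1 day (for example C&W faster, PN to 135). So if PN stops at 100–135 the coded age is 1 to 4 days early. The 1-day end is partly a counting convention, since PN to 150 gives the same gap when its last day is the day before.

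**A later PN course.** Assumed dates for illustration: full feeds on day 10, a later course on days 30 to 34. The coded age is 34, an error of 34 − 10 = 24 days.

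**The two codings together.** For an infant with one continuous PN course from enrolment day e to last day L, the first outcome is L − e + 1 and the second is L. Apart from the day of enrolment, they are the same quantity. If PN runs to full feeds, the withheld count is wrong; if it stops earlier, the full-feeds age is wrong too.

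**The case against.** The strongest reply is that PN is a disclosed, practical proxy. PN is named in the daily list and enteral volume is not, and in an open-label trial a PN record depends less on judgement than a decision to withhold feeds. Renaming the outcomes as total PN days and age at last PN would cure the mismatch with no new data. This largely stands as an argument for keeping the PN measures, but not under their present names.

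Further points on that side also hold:
- A reader might infer that the direct data for both outcomes are already collected. That is true for nil by mouth, not for age at full feeds. The fortifier start does not supply the date, because it also needs at least 50 ml of mother's own milk (section 7). Nor does the first targeted blood sample, which is Newcastle only, needs specific consent and is tied to clinical sampling (11.2.3).
- Nil-by-mouth days are not a perfect substitute. The outcome speaks of feeds withheld on any occasion, which may include days when only some feeds were held.
- A reader might infer that every infant gains 6 to 9 false days. That holds only for enrolment on day 1 with PN running to 150 ml/kg/day.
- A reader might infer a biased comparison between arms, because section 4.3 cites a trial with less necrotising enterocolitis on a human milk-derived fortifier. The documents give no frequency of late PN and no PN rule. Allocation is minimised on hospital site (9.5), so differences in site schedules should be roughly balanced. If diet does alter late PN, age at last PN reflects a real downstream effect; the fault is then its label.
- Section 12 uses a different name, feeding intolerance, within a safety list. It is a related outcome that needs reconciling, not a direct contradiction of 8.2.2.

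**Conclusion.** The point holds as a fault of outcome coding. Read literally, 8.2.2 scores PN days during uninterrupted advancement as withheld: about 3 to 9 days after enrolment if PN runs to 150 ml/kg/day, and 1 to 8 if it stops at 100–135. It also lets any later PN course replace a full-feeds age already reached, or places that age 1 to 4 days early if PN stops before 150. These sizes rest on the two site schedules in Appendix 1, feeds starting on day 1, enrolment on day 1 to 4 and the assumed PN stop volumes. How often late PN occurs cannot be derived from the protocol.

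The reach is limited. Two of the four feeding outcomes are affected, both secondary, in a trial that section 4.4 says is neither designed nor powered for clinical outcomes. Primary endpoints and sample size do not change. Bias between arms through late PN is possible but not shown. The outcomes should still be corrected, because the reported values would not mean what their names say.

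**What to change.** Revise 8.2.2, and reconcile section 12 with it, as follows:
- Count withheld days after enrolment from the daily nil-by-mouth record, and state that days with only some feeds held are not captured. Use the same wording in section 12.
- Report total PN days and age at last PN as outcomes in their own right, under those names.
- Code age at full feeds as the first time the criterion of at least 150 ml/kg/day for 3 days is met, using one added date item on the case report form, and state which of the three days supplies the age. Section 11.1 already allows case report forms where the national database lacks an item. If the item cannot be added, report age at the end of the first PN course, labelled as that. This removes the late-course error but remains a PN measure.

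The cost is revised wording, one extra case-report item and the loss of a derivation from the PN field alone. The change concerns outcome coding only, not feeding or PN practice.

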9.3. Screening and enrolment

Parents can be approached for consent at any time in the first few days after birth as long as babies remain eligible. Additionally, women in threatened preterm labour or with conditions likely to result in preterm delivery before 30 weeks of gestation will be approached antenatally to give them information about the study. An explanation will be given by GCP trained research staff, followed by written information and an opportunity to ask questions.

Parents will have as much time as they require provided the infant still remains eligible.

The study will only recruit preterm infants born at a gestational age of <30 weeks. We will approach parents for consent in the first 3 days after delivery but recognise that many mothers of potential infants may be in-patients on antenatal wards or attending fetal medicine clinics, and it is considered good practice to inform these families of potential research studies in advance. Use of a gestational age cut off facilitates this process.

522 523

524

525

526

527

528

529

530

531

532

9.4. Informed consent

"Informed consent" requires individual discussion with the infant's parents about the nature of the research to be conducted in a language that is easy to comprehend. The parents will have the study verbally explained to them and also be given a written information sheet about the study. The parents will understand that the infant can be allocated to one of two groups and that the trial is comparing two nutritional regimens. The parents will also understand that refusal to participate in the study will not affect the quality of subsequent medical care and if they do consent to participate, they may withdraw at any point without affecting their infant's care.

533 534

Before any trial-related procedures may be performed, informed consent must be obtained from the infant's parents by a trained member of the investigator team by means of a signed declaration. The investigator must record in the medical notes that informed consent was obtained and store the original signed declaration of consent in the patient's notes. A copy should be given to the infant's parents and a copy filed in the investigator file.

Written consent will be obtained once the baby is born and will explicitly state the intention

Written consent will be obtained once the baby is born and will explicitly state the intention to collect biological samples and the approach to randomisation. Parents may subsequently decline specific aspects of the study e.g. the collection of the targeted blood sample or MRI scan but still continue to participate in other aspects of the trial.

